4.2.8.3 Laboratory Data

Laboratory data (clinical chemistry, haematology and urinalysis) will be summarized and listed. Laboratory data outside the reference ranges will be indicated in the listings. If a subject has multiple results for a particular test at a particular time point, the first non-missing scheduled value will be used for the summary. System international (SI) units will be reported for all analytes.

Laboratory data absolute and change from baseline values for continuous chemistry, haematology and urinalysis parameters will be summarized at each scheduled assessment time. Separate tables will be provided for the SSO, restricted to visits during the open-label period and presented overall and for the SSR which will include all visits and be presented by treatment received during the randomized placebo-controlled period.

Shift tables will be provided for select tests, where shift from baseline to the maximum value will be summarized. These will be provided separately for the SSO which will be limited to visits during the open-label period and the SSR which will summarize the worst overall value across all visits. Shift tables for laboratory values by worst common toxicity criteria (CTC) grade will be produced for all parameters with grading. These will be provided separately for the SSO which will be limited to visits during the open-label period and be presented overall and the SSR which will summarize the worst CTC grade across all visits and be presented by treatment received during the randomized-withdrawal period.

In addition, the number and percentage of subjects with markedly abnormal clinical laboratory values will be summarized for each parameter by timepoint. These will be provided separately for the SSO, which will be limited to visits during the open-label period and be presented overall, and the SSR, which will summarize abnormal clinical laboratory values across all visits and be presented by treatment received during the randomized placebo-controlled period.

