3.4.2 Adverse Events

Adverse events (AEs) and Serious adverse events (SAEs) will be collected from start of the open-label correction phase, throughout the treatment period and including during the follow-up period. In addition, SAEs will be recorded from the time of signing the informed consent form and will continue throughout the clinical study until the end of any follow-up prior; this applies even if the subject has not received any study treatment (as per the SOP: Reporting of Individual Safety Events in Clinical Studies). SAEs which occur after the end of the clinical study but with a suspected causal relationship to the IP will be reported by the investigator but will not be included in summary tables and listings.

A treatment emergent AE (TEAE) will be defined as an AE with the start date on or after the first dose date and up to (and including) 7 days after the last dose date or an AE which starts prior to first dose of IP (i.e. before study day 1) which subsequently worsen in severity on or after the date of first dose of IP and up to and including 7 days following the date of last dose of study medication. AEs which occur more than 7 days after the last dose date will only be listed. Similarly, the number of patients experiencing SAEs, AEs that led to withdrawal, AEs that led to death and treatment related AEs, and number of such events, will be summarized by treatment group.

AEs will be further categorized as either occurring during the open-label period, if the start date is on or after the first dose date during the open-label correction period and prior to the date of the first dose of treatment during the randomized placebo-controlled period, or occurring during the randomized placebo-controlled period if the start date is on or after the date of the first dose of treatment during the randomized placebo-controlled period.

The Medical Dictionary for Regulatory Activities (MedDRA) (using the latest or current MedDRA version) will be used to classify AEs system organ class (SOC) and preferred term (PT).

If the relationship to treatment is missing, then the AE will be considered as possibly related to treatment.

Other significant adverse events

An overview of edema-related events (grouped terms include preferred terms of edema, edema peripheral, generalized edema, fluid overload, fluid retention, hypervolemia, localized edema, and peripheral swelling)and instances of sK+ <3.5 will be presented.

Deaths

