3.4.3 Laboratory Data

Absolute change from baseline in haematology and clinical chemistry variables will be calculated for each post-dose visit. CTC and maximum post-baseline grade will be calculated at each visit, where appropriate. Absolute values will be compared to the local laboratory reference range and classified as low (below range), normal (within range or on limits of range) and high (above range). All values classified as high or low will be flagged on the listings.

Urinalysis and blood for the determination of clinical chemistry and haematology will be taken at the visits indicated in the Schedule of Activities (SoA) Tables 1 of the CSP. Presentations and summaries will use central laboratory results except for urinalysis dipstick results which will be local. Laboratory parameters include:

Haematology/Haemostasis (whole blood)	Clinical Chemistry (serum)
B-Haemoglobin (Hb)	S-Creatinine (sCr)
B-Leukocyte count	S-Potassium (K+)
B-Leukocyte differential count (absolute count)	S-Bicarbonate (Total CO ₂)
B-Platelet count	S-Chloride (Cl-)
B-Hematocrit (Hct)	S-Glucose
	S-Creatinine
Urinalysis (dipstick, non central)	S-Blood Urea Nitrogen (BUN)
U-Hb/Erythrocytes/Blood	Urea (BUN)/Creatinine Ratio
U-Protein/Albumin	eGFR using the CKD-EPI formula
U-Glucose	Anion gap (blood, from POCT if available)
	S-Albumin
	S-Total Protein
	S-Calcium (Ca++)
	S-Magnesium (Mg++)
	S-Phosphate (PO ₄)
	S-Bilirubin, total
	S-Alkaline phosphatase (ALP)
	S-Alanine amino transferase (ALT)
	S-Aspartate amino transferase (AST)

Table 2: Laboratory Safety Variables

Estimated eGFR will be calculated using the CKD-EPI (chronic kidney disease epidemiology collaboration equation) formula for each time-point and will be analysed as provided by Covance Central Laboratory Services:

eGFR (CKD-EPI)= 141 x min(S_{Cr}/κ , 1)^{α} x max(S_{Cr}/κ , 1)^{-1.209} x 0.993^{Age} x 1.018 [if female] x 1.159 [if Black]

Where S_{Cr} (standardized serum creatinine) = mg/dL, $\kappa = 0.7$ (females) or 0.9 (males), $\alpha = -0.329$ (females) or -0.411 (males), min = indicates the minimum of S_{Cr}/κ or 1, max = indicates the maximum of S_{Cr}/κ or 1 and age = years. eGFR at study entry will be calculated based on either POCT or local laboratory creatinine values.

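### SAP Section 4.2.8.3 defines the laboratory shift tables by both the maximum and the worst value, and the maximum rule can leave a fall below range out of the table

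*SAP*

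**What the plan says.** Section 4.2.8.3 (Laboratory Data) introduces the reference-range shift tables with this sentence: "Shift tables will be provided for select tests, where shift from baseline to the maximum value will be summarized". The tests are not listed. The following sentence splits these tables by analysis set. The Safety Set Open version is limited to the open-label visits, and the other version is for "the SSR which will summarize the worst overall value across all visits", where SSR means the Safety Set Randomized.

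The categories come from Section 3.4.3, where values are "classified as low (below range), normal (within range or on limits of range) and high (above range". Table 2 in that section includes potassium, bicarbonate, haemoglobin, platelets, calcium, magnesium, albumin and eGFR, alongside creatinine, the transaminases and bilirubin.

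Section 4.2.8.3 also plans two further displays. The first is a separate set: "Shift tables for laboratory values by worst common toxicity criteria (CTC) grade will be produced for all parameters with grading". The second is a count: "the number and percentage of subjects with markedly abnormal clinical laboratory values will be summarized for each parameter by timepoint". Under other significant adverse events, Section 3.4.2 adds that "instances of sK+ <3.5 will be presented". Section 3.4.3 has all high and low values flagged in the listings.

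**The concern.** Two consecutive sentences give two rules for one table. A programmer who follows the first tabulates the largest value. One who follows the second tabulates the worst value. A third reading, maximum for the Safety Set Open and worst for the Safety Set Randomized, is also open. These readings produce different tables for any analyte whose abnormality is a low value.

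This matters more than usual here because the study drug lowers potassium, and the SAP itself singles out sK+ below 3.5 as a significant event. If potassium is among the selected tests and the maximum rule is applied literally, the table shows movement towards hyperkalaemia and largely omits movement towards hypokalaemia. The same holds for any other selected analyte where a fall is the concern, haemoglobin being an obvious candidate from Table 2.

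**Working it through.** The plan gives no figure to reproduce. The check compares the two rules under the SAP's own low, normal and high classes.

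**1. When the rules agree.** Take a patient's included post-baseline values for one analyte, and let LLN be the lower reference limit.

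- Under the maximum rule, the patient is classed low only if max < LLN, that is, only if every included value is low.
- Under a worst-value rule, for an analyte where a fall is the abnormality, the patient is classed low if min < LLN, that is, if any included value is low.
- The two differ whenever min < LLN ≤ max. Where a rise is the abnormality, worst and maximum are the same value and the tables agree.

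**2. Illustration for potassium.** The SAP gives no laboratory limits, so the normokalaemic range of 3.5 to 5.0 mmol/L is used here as an assumption. The patient values are hypothetical. Baseline is 5.5 (high).

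| Included post-baseline values | Maximum rule | Minimum | Worst value |
|---|---|---|---|
| 5.0, 3.2 | 5.0: high to normal | 3.2: high to low | 3.2: high to low |
| 5.0, 3.2, 5.1 | 5.1: high to high | 3.2: high to low | not determined |

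In both rows the maximum rule omits the value of 3.2. The second row shows that worst alone does not settle a two-sided analyte either. Section 3.1 ranks an out-of-range result above one within range, but it does not rank a low result against a high one.

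**3. The randomized set.** Under Sections 1.2 and 2.1, patients in the Safety Set Randomized reached K+ of 3.5 to 5.0 at the end of the open-label phase. That reading comes after the Day 1 baseline, and the table for this set spans all visits. If potassium is tabulated, nearly every patient therefore has at least one included value that is not low, and the maximum rule leaves the low column almost empty by construction. This rests on two assumptions: the laboratory's lower limit is near 3.5, and the central and POCT results taken at that visit are close.

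**4. What the other displays cover.**

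- The CTC shift tables use the worst grade, for graded parameters only. The SAP does not list which parameters are graded.
- The markedly abnormal counts cover each parameter by timepoint. They are not shifts from baseline, and this section gives no threshold.
- The presentation of sK+ below 3.5 covers potassium only.
- The listings flag every low value but are not summaries.

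Between them, these displays can show a fall. None of them settles which rule the shift table follows.

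**The case against.** A reader might infer that the laboratory shift tables as a whole run in the wrong direction for potassium, haemoglobin, magnesium and calcium, and that the safety output would therefore systematically hide hypokalaemia and look safer than the data. The SAP does not support that, for four reasons.

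- The maximum rule is attached to unnamed tests. All four analytes are in Table 2, but nothing shows that any of them is in this table. If only analytes with harm on the high side were selected, maximum and worst would agree.
- For potassium the maximum is incomplete, not wrong. Section 3.4.5 names both severe hypokalaemia (below 3.0 mmol/L) and severe hyperkalaemia (above 6.0 mmol/L), and in a placebo-controlled hyperkalaemia trial the upper direction is relevant.
- Falls have other routes into the report: the worst-grade shift tables, the markedly abnormal counts, the sK+ presentation, the visit-by-visit changes and the flagged listings.
- The text leans towards worst in places. Section 3.1 uses the worst value within each window for categorical summaries, and Section 4.2.8.3 uses it for the randomized set.

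It would also go too far to say that a single low value among some fixed number of readings can never appear. Section 3.4.3 leaves the sampling visits to the protocol's schedule, and the statement holds only for this table, under the literal maximum rule, when another included value is not low. The study also ended early with a small sample, which makes the listings easier to read patient by patient.

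All of this limits the consequence. It does not remove the conflict, and leaving the tests unnamed is part of the defect, because it prevents anyone from confirming that the maximum suits them.

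**Conclusion.** The point holds as a contradiction in one descriptive safety display. The maximum and worst rules in Section 4.2.8.3 give the same table only for analytes where a rise is the abnormality. For any selected analyte where a fall matters, or where both directions matter, the maximum rule drops a fall below range as soon as one other included value is normal or high.

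No endpoint, test or estimate of efficacy is touched, and falls can still be seen elsewhere in the safety output. The practical consequence for potassium depends on its being among the selected tests, which the SAP neither states nor excludes. The correction is still worth making: the drug lowers potassium, the SAP lists low potassium as a significant event, and the repair is cheap.

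**What to change.** In Section 4.2.8.3:

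- Name the tests for which reference-range shift tables will be produced.
- Replace the maximum value with a direction stated for each named test: shift to the minimum, shift to the maximum, or both where both directions matter, as for potassium.
- Use the same rule and wording for the Safety Set Open and the Safety Set Randomized, and remove the undefined worst overall value from this sentence.

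The cost is a change of SAP wording and a few extra tables from data already planned for collection. Nothing changes in alpha, sample size or trial conduct.

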1.2 Study design

This is a prospective, randomized, double-blind, placebo-controlled, parallel, multicenter, Phase IIIb study to investigate the safety and efficacy of SZC in patients with hyperkalemia and low bicarbonate (or metabolic acidosis).

The study will be conducted in the United States (US) at approximately 35 investigative sites.

This study consists of a short screening visit (Day 1), an open-label correction period (up to 48 hours), a 4-week randomized treatment period, and a follow-up period (7 days after the last administration of study medication). The total study treatment duration, consisting of open-label and randomized periods, will be 29 days.

Screening will be performed using potassium and bicarbonate value from a study-approved point-of-care test (POCT) to determine eligibility of consenting patients to enter the openlabel correction phase. Patients who meet the POCT eligibility criteria of serum potassium (sK+) between 5.1-5.9 mmol/L inclusive, AND serum bicarbonate between 16-20 mmol/L inclusive, will be enrolled into the open-label correction phase. All baseline parameters should be measured/collected prior to administration of the first dose of study drug in the open-label initial phase.

In the open-label initial phase, patients will receive open-label SZC orally at a dose of 10 g three times daily (TID) for up to 48 hours, depending on POCT potassium value.

Patients who achieve normokalemia (K+ between 3.5 and 5.0 mmol/L inclusive) within 24-48 hours will be randomized 1:1 into the double-blind randomized treatment phase to receive 10 g SZC or placebo once daily (QD) starting dose for the following 28 days. Patients who achieve normokalemia after 24 hours will be randomized and will not need to continue on 10 g SZC TID for another 24 hours.

Study treatment will end with the Day 29 visit, which will be followed by the end of study visit 7 days after the last administration of study medication.

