2 ANALYSIS SETS

2.1 Definition of analysis sets

Screened Set

All subjects who were screened for inclusion in the open-label run-in period of the study. This analysis set will be used to describe the demographics of subjects considered for inclusion in the study. The assignment of subjects to a treatment group for analysis is not applicable.

Safety Set Open

All patients enrolled in the open-label correction phase who took at least 1 dose of study drug. The Safety Set Open (SSO) analysis set will be used to describe the safety characteristics of SZC during the open-label period. Patients will be analyzed as a single group.

Safety Set Randomized

All patients who achieve normokalemia at the end of the open-label correction phase and who received at least one dose of either SZC or placebo during the randomized placebo-controlled phase. The Safety Set Randomized (SSR) analysis set will be used to describe the safety characteristics of SZC or placebo during the randomized placebo-controlled phase. Patients will be analyzed according to the investigational product (IP) received during the randomized placebo-controlled phase.

Full Analysis Set

All patients who achieve normokalemia (K+ between 3.5 and 5.0 mmol/L inclusive) at the end of the open-label correction phase and enter the randomized placebo-controlled phase. The Full Analysis Set (FAS) will be the primary analysis set used for the primary, secondary and CCL Patients will be analyzed on an intent-to-treat basis according to their randomized IP.

Per Protocol Set

The Per Protocol Set (PPS) is defined as all patients in the FAS without any important protocol deviations leading to exclusion from the PPS. Patients will be analysed according to their randomized IP. The PPS will be used for sensitivity analysis of the primary and secondary endpoints.

Protocol deviations are defined as any change, divergence, or departure from the study design of procedures defined in the clinical study protocol (CSP). Important protocol deviations are a subset of protocol deviations and may significantly impact the correctness, accuracy, and/or reliability of the study data or that may significantly affect a subject's rights, safety, or wellbeing. Important protocol deviations which should lead to exclusion from the PPS will be defined by the Sponsor before database lock by judging the importance of the deviations upon the primary efficacy endpoint.

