4 ANALYSIS METHODS

The principal analyses outlined in this statistical analysis plan will be conducted by Covance Inc., in accordance with the contract with AstraZeneca Pharmaceuticals LP and following the Excellence in Medical Partnership for Outsourced Worldwide Evidence Research (EMPOWER) description of services.

The below mentioned general principles will be followed for analyses:

Descriptive statistics will be used for all variables, as appropriate. Continuous variables will be summarised by the number of observations, mean, standard deviation, median, Q1, Q3, minimum and maximum. Categorical variables will be summarized by frequency counts and percentages for each category.

Unless otherwise stated, percentages will be calculated out of the analysis set total for the treatment group.

For continuous data, the mean and median will be rounded to 1 additional decimal place compared to the original data. The standard deviation will be rounded to 2 additional decimal places compared to the original data. Minimum and maximum will be displayed with the same accuracy as the original data.

For categorical data, percentages will be rounded to 1 decimal place.

SAS® version 9.3 or higher will be used for all analyses

It is acceptable to present large numerical values in more appropriate units. For example, an AUC value of 123,000 ng h/mL may be reported as 123 μ g h/mL instead. It is however, important to keep the units consistent within the report and the precision consistent with that prior to conversion.

In general, for all endpoints the last observation before the first dose of study treatment in the open-label period will be considered the baseline measurement, unless otherwise specified. For assessments on the day of first dose, where time is not captured, a nominal pre-dose indicator, if available, will serve as sufficient evidence that the assessment occurred prior to first dose.

Assessments on the day of the first dose when neither time nor a nominal pre-dose indicator are captured will be considered prior to the first dose if such procedures are required by the protocol to be conducted before first dose.

In all quantitative summaries from baseline, variables will be calculated as the post-treatment value minus the value at baseline. The percentage change from baseline will be calculated as (post-baseline value – baseline value) / baseline value x 100. Absolute and percentage change will be summarized.

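### The SSR laboratory shift tables take the worst value and worst CTC grade over every visit, so abnormalities arising during open-label SZC can be counted under placebo and SZC alike

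*SAP*

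**What the plan says.** Section 4.2.8.3 of the SAP plans two kinds of laboratory shift table, each produced separately for the SSO and the SSR. The SSO versions are limited to open-label visits. The SSR version of the worst-value table is for "the SSR which will summarize the worst overall value across all visits". The SSR version of the CTC table is for "the SSR which will summarize the worst CTC grade across all visits and be presented by treatment received during the randomized-withdrawal period". The period named at the end of that last quote can only be the randomized placebo-controlled period, since the SAP defines no other randomized period.

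Four other places bear on this:

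- Section 1.2: in the open-label phase "patients will receive open-label SZC orally at a dose of 10 g three times daily (TID) for up to 48 hours". This includes everyone later given placebo.
- Section 4: "the last observation before the first dose of study treatment in the open-label period will be considered the baseline measurement". Shifts are therefore measured from a value that precedes the open-label dosing.
- Section 2.1: "The Safety Set Randomized (SSR) analysis set will be used to describe the safety characteristics of SZC or placebo during the randomized placebo-controlled phase".
- Sections 3.4.2 and 4.2.8.1: adverse events are assigned to a period by the first randomized dose, and the SSR adverse event tables include only events from the randomized period.

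On reference ranges, section 3.4.3 states "Absolute values will be compared to the local laboratory reference range" and, a few lines later, "Presentations and summaries will use central laboratory results except for urinalysis dipstick results which will be local".

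**The concern.** A worst-value table reduces all of a patient's post-baseline results to one. If the window includes results obtained on open-label SZC, the reported worst may belong to that exposure while the column heading names the later treatment. For a placebo patient, the table would then show under placebo a result obtained on active drug.

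Two things are at stake. The SSR shift tables would not describe the phase that section 2.1 says the SSR is meant to describe. The laboratory and adverse event tables for the same set and the same columns would also cover different exposure, with no reason given. Because the open-label experience is common to both arms, it adds a similar background to each, and a relative excess in either arm looks smaller than it is.

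The reference-range wording raises a smaller question of the same kind. High and low flags, and any shift table built on them, depend on which laboratory's limits are applied to a central result.

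**Working it through.** No figure in the SAP is at issue, so there is nothing to reproduce. The check has two parts.

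**1. Does the text let open-label values in?**

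- The visit limit for the SSO and the all-visit scope for the SSR are set against each other in the same sentence of section 4.2.8.3. Reading the SSR scope as randomized visits only would remove that contrast. For the continuous summaries the section uses the same contrast: a table "for the SSR which will include all visits and be presented by treatment received during the randomized placebo-controlled period".
- Section 3.4.3 grades results after baseline, and baseline precedes open-label dosing, so open-label results are not removed by the derivation.
- Limiting the tables to visits labelled Randomized in Table 1 (section 3.1) would not be enough. Visit 3 is the randomization visit. It follows open-label dosing, yet Table 1 assigns it to the Randomized period. The cut has to be the first randomized dose.
- An example follows from the design. A patient randomized at 48 hours rather than 24 was not yet normokalemic by POCT at about 24 hours, and section 3.3.1 has central samples drawn at the same time points. If potassium is among the tests selected for shift tables, that open-label result can be the patient's maximum whatever happens after randomization.

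**2. How much could it matter?**

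The SAP gives no laboratory abnormality rates, so all rates below are assumptions. Let *r* be the chance of an abnormal value in the randomized phase and *o* the chance in the open-label phase, equal in both arms and independent of *r*.

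- Displayed rate = 1 − (1 − *r*)(1 − *o*)
- Displayed risk difference = (1 − *o*) × (*r* for SZC − *r* for placebo)

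Take *r* = 6% for SZC and 2% for placebo. With *o* = 5%:

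- SZC: 1 − 0.94 × 0.95 = 0.107
- Placebo: 1 − 0.98 × 0.95 = 0.069
- Risk ratio: 0.107 / 0.069 = 1.55
- Risk difference: 0.95 × 4.0 = 3.8 points

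| Open-label rate *o* | SZC shown | Placebo shown | Risk ratio | Risk difference (points) |
|---|---|---|---|---|
| 0% (restricted table) | 6.0% | 2.0% | 3.0 | 4.0 |
| 3% | 8.8% | 4.9% | 1.79 | 3.9 |
| 5% | 10.7% | 6.9% | 1.55 | 3.8 |
| 10% | 15.4% | 11.8% | 1.31 | 3.6 |

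A second set of assumptions gives the same pattern. With 10% against 2%, the risk ratio of 5.0 becomes 2.98, 2.10 and 1.61 at *o* = 2%, 5% and 10%. At the planned 68 per arm, the expected placebo patients shown as abnormal rise from 1.4 to 2.7, 4.7 and 8.0. The absolute difference moves from 8.0 to 7.8, 7.6 and 7.2 points.

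**The case against.** The best counter-argument is that the damage is modest and mostly visible elsewhere.

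- **The absolute contrast barely moves.** It is multiplied by (1 − *o*), so 4.0 points becomes 3.8 at a 5% open-label rate. The tables are descriptive, and no risk ratio or test is planned on them. This stands. A reader might infer that the rule hides a drug–placebo difference or favours one arm. The documents do not support that: the open-label contribution is equal in expectation in both arms, so the result is inflated counts and a diluted ratio.
- **Not every laboratory table is affected.** A reader might extend the point to the markedly abnormal values. Section 4.2.8.3 presents those by time point, so open-label and randomized visits stay apart.
- **Cause is not shown.** It is tempting to say that open-label SZC caused these abnormalities. Worst-value tables do not assess cause, and the patients have CKD. Only the timing is established.
- **The rates are assumed, and potassium is a special case.** SSR patients must be normokalemic at the end of the open-label phase, so low potassium at that point should be rare apart from disagreement between POCT and central results. Entry potassium and bicarbonate are abnormal by design, and a shift table displays baseline status. All this limits the size for those analytes. It does not remove the problem for other tests, or for an open-label potassium value still high at 24 hours.
- **Sampling at Visits 2 and 3 is set by the protocol's schedule, which is not at hand.** The effect is confined to tests drawn at those visits.
- **By-visit summaries, SSO tables and listings let a reader trace the timing.** That is true, but a summary table should not need the listings to correct its column headings.

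**Conclusion.** The point holds for two tables: the SSR worst-value shift table and the SSR worst-CTC-grade shift table. As written, both admit results obtained on open-label SZC and report them under the later treatment, contrary to section 2.1 and to the adverse event rule in sections 3.4.2 and 4.2.8.1. That conclusion rests on the SAP's wording alone.

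The size does not. It rests on assumed rates, equal open-label risk in the two arms and independence between phases. Under those assumptions, with 6% against 2%, an open-label rate of 3% to 10% takes the risk ratio from 3.0 to between 1.79 and 1.31, while the risk difference stays between 3.9 and 3.6 points. Since the study ended early and fewer patients are available, a handful of carried-over results could make up much of what these tables show. The change should be made, but the flaw does not undermine the safety evaluation as a whole.

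The reference-range wording is a separate, secondary inconsistency. Applying local limits to central results can misclassify values as high or low; its size cannot be judged from the SAP.

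**What to change.** In section 4.2.8.3, restrict the SSR worst-value and worst-CTC-grade shift tables to assessments after the first randomized dose, through the last follow-up assessment (Visit 8). Three details matter:

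- Define the lower limit by the first randomized dose and not by Table 1's period label, because Visit 3 carries the Randomized label.
- Do not borrow the adverse event rule's upper limit of 7 days after the last dose. With dosing ending at about Day 29, that limit falls at about Day 36, while the Visit 8 window runs from Day 33 to Day 39, so valid follow-up results could be lost.
- Keep earlier values in the SSO tables and in the by-visit columns. Section 4 limits SSO analyses to Visits 1 and 2, so say explicitly where Visit 3 results obtained before the first randomized dose are shown.

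The markedly abnormal table needs no change. In the same edit, replace the stray period name in the CTC sentence with the randomized placebo-controlled period.

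In section 3.4.3, state that central results are classified with the central laboratory's reference ranges, and keep local ranges for the dipstick results.

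The cost is a few sentences of SAP text and a date filter in two tables. No new data are needed.
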